#### **Primary outcome: Cognitive impairment**

Measures:

Montreal Cognitive Assessment (MOCA) (10 minutes) A validated screening tool for detection of mild cognitive impairment.

BrainCheck Neurocognitive Assessment (15 minutes): FDA-approved validated automated remote neurocognitive assessments in multiple domains.

ImPACT (20 minutes) is an FDA-approved computerized neurocognitive concussion assessment tool.

Secondary outcomes: depression (PHQ8), satisfaction with life (SWLS), disability (Sheenan Disability Scale), and health care utilization (ED and outpatient visits).

Statistical Analysis:

Aim 1: Intent-to-treat analyses stratified by depression severity. We evaluate three-month outcomes using linear regression models with assigned intervention depression severity and the corresponding baseline score as independent variables. Longitudinal linear mixed effects regression models with time, intervention, depression severity and corresponding baseline scores will assess treatment effects at 1.5 and 3 months and with interactions between intervention and time-points tested. Multivariable models include prespecified demographic and COVID symptom characteristics as covariates.

Aim 2: We will build a seamless Phase 2 to Phase 3 design with defined decision rules to determine whether interventions, including dCBT and stimulant, will “graduate” to the Phase 3 adaptive clinical trial. Bayesian analyses of accumulated data (including data from Aim 1) are performed on a prespecified schedule until stopping criteria are met. For a comparison of interventions, we may conclude superiority, inferiority or futility which can depend on pre-defined stratification variables. We anticipate that a response adaptive randomization (RAR) will be applied in Phase 3 such that the proportion of participants who receive each intervention will be determined based on the predicted probability that the intervention is optimal considering all accrued outcome data. Findings from Aim 1 will be used in simulations to estimate sample size requirements and to evaluate the operating characteristics of the adaptive clinical trial.

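### The plan does not say which of three cognitive instruments gives the primary score, or which treatment contrast is primary when the hypothesis reverses direction by depression group

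*Combined protocol and SAP*

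**What the plan says.** The section headed "Primary outcome: Cognitive impairment" lists three instruments under Measures:

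- MOCA: "A validated screening tool for detection of mild cognitive impairment".
- BrainCheck: "FDA-approved validated automated remote neurocognitive assessments in multiple domains".
- ImPACT, which "is an FDA-approved computerized neurocognitive concussion assessment tool".

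No score or domain is named for any of them. The Project Summary and Aim 1 (Summary of Project) repeat the construct without choosing an instrument.

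Under Statistical Analysis, Aim 1 begins "Intent-to-treat analyses stratified by depression severity" and continues "We evaluate three-month outcomes using linear regression models with assigned intervention depression severity and the corresponding baseline score as independent variables". A mixed model for the 1.5- and 3-month values follows, "with interactions between intervention and time-points tested". The two models are not ranked. No alpha, success criterion or multiplicity rule is given for Aim 1.

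The hypothesis in Summary of Project is directional and differs by group: stimulant is expected to be better in patients with cognitive impairment alone, and dCBT in those who are also depressed. Randomization is 1:1 and stratified by depression severity.

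**The concern.** Two choices that decide the primary result are left open.

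**The score.** Three instruments share one primary outcome, and BrainCheck alone covers several domains. The reference to a corresponding baseline score suggests one regression per instrument. That would give at least three primary results and no rule for reading them together. If they disagree, the conclusion depends on a choice made after the data are seen.

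**The contrast.** The hypothesis is about effects that point in opposite directions in two groups. The listed regression contains intervention, depression severity and baseline score, and the only interaction that Aim 1 names is with time. If stratified means adjusted for depression, the model estimates one pooled effect, and that does not test the hypothesis. If it means analysed within each group, the hypothesis is addressed. The text does not say which is meant, or whether one group or both must succeed.

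**Working it through.** **1. The plan's own figure.** The only size given is 120 patients (Project Summary). It cannot be reproduced, because no alpha, power, SD or target difference is stated for a cognitive score. For orientation, 60 per arm with one score, one overall contrast, two-sided 5% and 80% power (all assumed) detects √(2/60) × (1.960 + 0.842) = 0.183 × 2.802 = 0.51 SD.

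**2. Three instruments.** Assumed: each tested at two-sided 5%, test statistics jointly normal with one common correlation ρ. The chance under the null that at least one is significant is 1 − P(|Z1|, |Z2|, |Z3| all below 1.96). At ρ = 0 this is 1 − 0.95³ = 14.3%; the others are by numerical integration.

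| ρ | 0 | 0.5 | 0.7 | 0.8 | 0.9 | 0.95 |
|---|---|---|---|---|---|---|
| Any of three wins | 14.3% | 12.5% | 10.9% | 9.8% | 8.4% | 7.3% |

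If all three must win, the error stays below 5% (at most 3.0% under the joint null over these values of ρ).

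**3. Pooled contrast against interaction.** Inputs: 120 patients; 1:1 allocation (Summary of Project); 46% depressed (Problem statement). Assumed: two-sided 5%, no dropout, no gain from baseline adjustment.

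- Per arm: 0.46 × 60 = 27.6 depressed and 0.54 × 60 = 32.4 not depressed.
- Pooled effect = 0.54 × (effect in not depressed) + 0.46 × (effect in depressed), with SE √(2/60) = 0.183.
- Interaction SE = √(2/27.6 + 2/32.4) = 0.366.
- Power = Φ(effect/SE − 1.96) + Φ(−effect/SE − 1.96).

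In every row the strata differ by 1.0 SD, so the interaction test has power Φ(1.0/0.366 − 1.96) = 78% throughout.

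| Not depressed / depressed (SD) | Pooled effect (SD) | Pooled power |
|---|---|---|
| +0.5 / −0.5 | 0.270 − 0.230 = 0.04 | 6% |
| +0.6 / −0.4 | 0.324 − 0.184 = 0.14 | 12% |
| +0.7 / −0.3 | 0.378 − 0.138 = 0.24 | 26% |
| +0.8 / −0.2 | 0.432 − 0.092 = 0.34 | 46% |

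The 48% depressed quoted in the Project Summary changes the first row to 0.02 SD and 5%. A share of 30% or 70% with ±0.5 SD gives a pooled effect of 0.20 SD in size and about 20% power.

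**4. Within-stratum contrasts.** The detectable difference at 80% power is √(2/n) × (z for alpha + 0.842), with √(2/27.6) = 0.269 and √(2/32.4) = 0.248.

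| Alpha | Multiplier | Depressed | Not depressed |
|---|---|---|---|
| 5% | 2.802 | 0.75 SD | 0.70 SD |
| 2.5% (first Holm step) | 3.083 | 0.83 SD | 0.77 SD |

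Two unadjusted stratum tests, either counting as a win, have an error rate of 1 − 0.95² = 9.75%. At 0.5 SD in each stratum, power at 2.5% is 35% (depressed) and 41% (not depressed), so the chance of at least one Holm rejection is 1 − 0.65 × 0.59 = 62%.

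**The case against.** The best defence has five parts.

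- **The comparison is named.** The plan gives the two treatments, the expected direction in each depression group, the 3-month time point and a baseline-adjusted model. This stands. A reader might infer that no treatment contrast is defined at all, and the documents do not support that. What is missing is which contrast is primary.
- **Stratified can mean within group.** That is an ordinary use of the word, it fits the hypothesis, and it removes the pooling problem. This stands as a possible reading, but the text does not settle it. The sentence listing the covariates also lacks punctuation between intervention and depression severity. The parallel list for the mixed model, which separates the two, makes a lost comma more likely than an intended interaction. Aim 1 does include assessing how demographic and COVID symptom variables affect treatment efficacy, so effect modification is not ignored, but depression is not named there.
- **Cancellation is not inevitable.** The hypothesis gives directions, not equal sizes, so 6% power is close to the worst case. This stands, and the range in the working reflects it. The depressed share among patients who meet the trial's own entry criteria is also unknown, because both quoted shares describe clinic patients.
- **No any-one-wins rule is written.** Correct. The 10-13% shows what one permitted reading would cost; it is not the plan's error rate.
- **The trial is preliminary.** The Problem statement says so. That lowers the stakes, but Aim 1 is still framed as a test of efficacy, and its data carry forward: "Bayesian analyses of accumulated data (including data from Aim 1) are performed on a prespecified schedule until stopping criteria are met". A reader might infer that Aim 2 cannot proceed without a single outcome. The documents do not say that, and the point does not rest on it.

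None of these supplies a primary score. The decision rules under Aim 2 concern the later adaptive design and give no threshold for Aim 1.

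**Conclusion.** The concern holds in two parts of unequal strength.

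**Endpoint (high confidence).** Nothing in the available text says which score is primary, whether the instruments are combined, or how multiplicity is controlled. Run as written, the plan yields at least three primary results with no rule to reconcile them. The size of the problem depends on an unstated win rule: no inflation if all must win, about 10-13% if any may win at plausible correlations.

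**Contrast (moderate confidence).** Which contrast is primary is open. If stratified means adjusted, the pooled comparison does not test the stated hypothesis, and its power for opposite effects depends heavily on their relative size. If it means within group, what remains missing is the success rule across the two groups. A reader might conclude that the trial is bound to miss its own hypothesis; that follows only under the adjusted reading with nearly equal and opposite effects.

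All error and power figures are illustrations on assumed inputs, because the plan states no alpha, sidedness, effect size or dropout rate. They do not contradict any figure in the plan.

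**What to change.** Before outcome data are examined, add to Statistical Analysis, Aim 1:

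> The primary endpoint is [one instrument and score, chosen by the sponsor] at 3 months, analysed by linear regression on assigned intervention, depression stratum, their interaction and the baseline score. The primary contrasts are the intervention effect within each depression stratum, tested with Holm at familywise two-sided 0.05. The interaction estimate and its confidence interval are also reported. The other two instruments, the 1.5-month values and the pooled arm comparison are secondary.

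The depression cut-off that defines the strata should be stated with it, as the plan gives none. One prespecified z-score composite is an acceptable alternative endpoint, but it is less directly interpretable and needs a rule for a missing instrument.

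An interaction test that must succeed before the strata are examined should not lead. If one treatment were better by 0.5 SD in both groups, the true interaction would be zero and that gate would open only 5% of the time, while a pooled test has power Φ(0.5/0.183 − 1.96) = 78%. If the effect were 0.7 SD in the non-depressed and zero in the depressed, simulation shows the gated procedure finding it 46% of the time, against about 80% for the ungated stratum test at 5%.

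The change uses data already planned and is mainly wording. It has two costs: the demoted instruments and the pooled comparison can no longer support a primary claim, and only fairly large stratum effects (0.70-0.83 SD, step 4 of the working) are detectable at 80% power with 120 patients.

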#### **Select the item(s) that best support(s) your research**

- ✓ **Promotes research with new approaches and innovations in care.**
- ✓ Incorporates the concept of comparative effectiveness and/or embedded and **adaptive designs**, which allows researchers to rapidly test multiple treatment approaches more efficiently than traditional clinical trials and with quicker, more applicable results.
- ✓ Supports a current UPMC focused initiative, including (but not limited to) those with aggressive approaches to cancer, gastrointestinal, heart disease **and neuroscience**.

**Problem statement:** (COVID-19 threatened the health of millions of Americans and others across the globe. After acute illness, prolonged effects called Long-COVID extract much from sufferers; data driven methods to address and manage these symptoms are lacking. Cognitive fog and emotional distress are common longer-term consequences after COVID-19. In our clinic, 80% of Long-COVID patients report persistent cognitive fog and 46% of these have at least moderate depressive severity. Both inflammatory and non-inflammatory factors may cause the cognitive and depressive symptoms.

We propose two efficient solutions that advance the treatment of reversible cognitive impairment secondary to COVID, which may apply to other medical conditions. ***Our two interventions approach the problem from different perspectives- one targeting cognitive fog associated with depression, the other the cognitive fog directly.*** For depression with cognitive fog, a digital cognitive behavioral solution with health coaches offers cognitive rehabilitation strategies. For cognitive fog without depression, a stimulant medication known to reduce cognitive impairment in other chronic medical conditions will be used. Preliminary findings from this project will provide the necessary data to write a competitive federally supported proposal to fund a larger-scale adaptive design study. This next phase proposal will also incorporate learnings from this preliminary study to personalize intervention strategies to target specific cognitive domains of impairment. We will seek both federal funding and internal funding (UPMC Enterprises) for this next larger phase.

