#### **Summary of Project**

Design Summary: Randomized trial of dCBT versus stimulant to treat cognitive impairment +/- depression in adults with Long-COVID.

Aim 1: Test efficacy of two interventions for improving cognitive impairment (primary outcome) and emotional distress (depression), life satisfaction, work disability, and medical utilization (secondary

outcomes). Assess effect of demographic and COVID symptom characterization variables on treatment efficacy.

Hypothesis: Stimulant therapy will outperform dCBT for patients with cognitive impairment alone and dCBT will outperform stimulant for cognitive impairment and depression.

Aim 2: Define the important response characteristics in these patients to inform design of a larger adaptive clinical trial evaluating treatment options for COVID-related cognitive impairment.

Methodology: Participants with confirmed Long-COVID cognitive impairment assigned with a 1:1 allocation to either arm using a permuted block design stratified by depression severity. Participants will complete computerized neurocognitive assessments and other study measures at baseline, 1.5 (interim) and 3 months after randomization.

Inclusion: Patients with Long-COVID between ages of 21-65; moderate cognitive impairment (MOCA $\leq$ 18) present for at least 3 months; access to a smartphone.

Exclusion: No history of dementia, psychosis, mania, addiction or current conditions requiring immediate hospitalization. No history of stimulant failure. No current cardiac condition

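### The hypothesis says the better treatment reverses with depression, but Aim 1 specifies no intervention-by-depression term and no within-stratum contrast

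*Combined protocol and SAP*

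**What the plan says.** Under Summary of Project, the hypothesis reads: "Stimulant therapy will outperform dCBT for patients with cognitive impairment alone and dCBT will outperform stimulant for cognitive impairment and depression". The problem statement gives the same rationale from the treatment side: "For cognitive fog without depression, a stimulant medication known to reduce cognitive impairment in other chronic medical conditions will be used". Randomisation is 1:1 by a "permuted block design stratified by depression severity".

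The Statistical Analysis text for Aim 1 opens with "Intent-to-treat analyses stratified by depression severity". It then specifies two models:

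- **Three-month outcome:** "linear regression models with assigned intervention depression severity and the corresponding baseline score as independent variables".
- **Repeated measures:** "Longitudinal linear mixed effects regression models with time, intervention, depression severity and corresponding baseline scores", with "interactions between intervention and time-points tested".

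The first list has no separator between intervention and depression severity. I read a missing comma, because the parallel list for the mixed model has commas and no depression interaction.

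Aim 1 also promises to "Assess effect of demographic and COVID symptom characterization variables on treatment efficacy", but the analysis text enters those characteristics only as covariates. The number of depression strata and their cut-off are not given.

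**The concern.** The hypothesis makes two signed claims, one per depression group, and together they describe a treatment effect that changes sign. To test it, the analysis must let the treatment effect differ by depression. The models as listed do not. They let depression shift the mean outcome, and they estimate one treatment effect averaged over both groups.

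That average does answer the general question of how the two treatments compare. It does not answer the hypothesis. If the hypothesis is true, a small pooled estimate could be read as no difference although the choice of treatment matters in both groups.

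The gap also reaches Aim 2. Findings from Aim 1 feed the simulations for the adaptive trial, where conclusions may depend on stratification variables. The plan does not say that stratum-specific estimates will be produced for that purpose. Contrasts chosen after the data are seen would be open to challenge as post hoc.

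The promise about demographic and COVID-symptom variables has the same weakness on a smaller scale. A covariate adjusts for prognosis; it does not show whether treatment works differently.

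**Working it through.** **What follows without assumptions.** Let *a* be the stimulant-minus-dCBT effect without depression and *b* the effect with depression, signed so that positive favours stimulant. The hypothesis says *a* > 0 > *b*. With depressed share *p*, the pooled effect is (1 - *p*)*a* + *pb*. It lies strictly between *a* and *b*, so it equals neither. It is either zero or has the wrong sign for one group.

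**Inputs from the documents.** N = 120; 1:1 allocation; depressed share 48% (Project Summary) or 46% (problem statement). Both are clinic shares, used here as proxies for the trial mix.

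**Inputs assumed.** The documents state no alpha, cognitive effect size, SD or dropout, so there is no plan figure to reproduce. I take two-sided 5%, effects in residual SD units, 120 completers, and a depressed share up to 50% as a sensitivity value.

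**Formulas** (non-central t):

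- Pooled: SE = √(4/N), df = N - 4.
- Stratum contrast: SE = √(4/n_s), df = n_s - 2.
- Interaction *a* - *b*: SE = √(4/n_dep + 4/n_non), df = N - 5.
- Both contrasts succeed: product of the two powers in the predicted direction.

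**At 48% depressed.** n_dep = 57.6 and n_non = 62.4. The SEs are:

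- pooled: √(4/120) = 0.183
- depressed: √(4/57.6) = 0.264
- non-depressed: √(4/62.4) = 0.253
- interaction: √(4/57.6 + 4/62.4) = 0.365

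For +0.5/-0.5 the pooled effect is (62.4 × 0.5 - 57.6 × 0.5)/120 = 0.020 SD.

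| *a* / *b* (SD) | Completers | Pooled effect | Pooled power | Interaction power | Both contrasts |
|---|---|---|---|---|---|
| +0.5 / -0.5 | 120 | 0.020 | 5.1% | 77.4% | 22.8% |
| +0.5 / -0.5 | 96 | 0.020 | 5.1% | 67.8% | 15.6% |
| +0.3 / -0.3 | 120 | 0.012 | 5.0% | 37.0% | 4.3% |
| +0.8 / -0.4 | 120 | 0.224 | 22.9% | 90.3% | 28.0% |
| +0.4 / -0.8 | 120 | -0.176 | 15.9% | 90.3% | 29.0% |
| +1.0 / 0 | 120 | 0.520 | 80.6% | 77.4% | 2.4% |

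**Range over 46% to 50% depressed, 120 completers.**

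- +0.5/-0.5: pooled effect 0.00 to 0.04 SD, power 5.0 to 5.5%.
- +0.8/-0.4: 0.20 to 0.25 SD, power 19 to 27%.
- +0.4/-0.8: -0.15 to -0.20 SD, power 13 to 19%.

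**Why the interaction alone is not enough.** In the last row of the table the hypothesis is false, because dCBT is not better in the depressed. The interaction test still rejects 77.4% of the time; both contrasts succeed only 2.4% of the time.

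**Precision at N = 120 (95% CI half-width).** Pooled 0.36 SD; each stratum 0.50 to 0.54 SD; interaction 0.72 to 0.73 SD.

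**Simulation check.** In 20,000 least-squares fits with 29 depressed and 31 non-depressed per arm at +0.5/-0.5, the mean pooled estimate was 0.017 SD with 4.7% rejections. The interaction was significant in 77.3% and both contrasts succeeded in 23.5%.

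**The case against.** The best defence is the opening phrase "Intent-to-treat analyses stratified by depression severity". It precedes the models and could govern them, so that each is fitted separately by stratum. That would give a treatment estimate in each group, and the dilution shown above would not arise. Severity as a regressor does not rule this out: a stratum indicator is constant within its stratum, but a continuous score is not, and the plan does not say which is meant. The missing separator in the three-month list also makes that list weaker evidence that a term is absent.

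This makes the dilution conditional on the pooled reading. It does not remove the problem. Even with separate fits, the plan names no stratum contrast as a result, defines no strata, and writes no test that the effects differ. Two analysts could follow the text and report different primary results.

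Three smaller points are fair:

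- **Pooled SE.** The formula ignores residual variance left by the omitted interaction. Allowing for it (residual SD about 1.03 to 1.04) lowers the +0.8/-0.4 pooled power from 22.9% to 21.4% and widens the pooled half-width to 0.37 to 0.38 SD. Neither changes the conclusion.
- **Strict success rule.** Requiring both contrasts to succeed is demanding for a preliminary trial. This stands, and it is why the contrasts should be reported mainly as estimates.
- **Other effect modifiers.** The demographic and symptom terms are a separate, optional matter.

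**Conclusion.** The concern holds. The plan states a sign-reversing hypothesis and does not specify an analysis that tests it. This much needs no assumed effect size. That the pooled effect describes neither group depends on two things: the pooled reading of the models, which is the more natural one, and the hypothesis being true. How close the pooled effect comes to zero depends on the assumed effects. It is nearly zero when they are equal and opposite, and about 0.15 to 0.25 SD in size in the unequal cases examined. This should be fixed. The stratum-level data would still exist, so the damage is recoverable, but prespecification would be lost.

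**What to change.** 1. Define the depression stratum once (levels and cut-off) and say what a stratified analysis means.
2. Add intervention by depression stratum to the three-month model. In the mixed model, add intervention by stratum by time with its lower-order terms.
3. Report the stimulant-minus-dCBT contrast in each randomisation stratum with a 95% CI as the direct test of the two claims, and the interaction as the formal test that the effects differ. Count the full hypothesis as supported only if both contrasts succeed in the predicted direction, which needs no alpha split. If either half may be claimed alone, state the multiplicity rule.
4. Keep the pooled effect as the overall comparison.
5. Carry the stratum estimates and their CIs into the Aim 2 simulations.
6. State the expected precision of the contrasts at N = 120.
7. Optionally, prespecify a short list of intervention by demographic or symptom terms as exploratory estimates with CIs.

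**Cost.** This is a change of wording; the stratum is already used for randomisation and no new data are needed. The price is precision. At 48% depressed, 80% power for both contrasts needs effects of about ±0.85 SD at N = 120, or about N = 336 at ±0.5 SD. N = 120 cannot firmly confirm both halves, so present the contrasts as estimates for the next trial.

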#### **Project Summary**

The multi-disciplinary UPMC Post-COVID Recovery clinic serves the clinical needs of Long-COVID patients, those with persistent symptoms after initial infection recovery. Using an IRB-approved research registry collecting biomarkers, clinical data, imaging results and patient-reported outcomes (PROs), this group defines burden of long-COVID and guides personalized medicine strategies.

To date, phenotyping of 148 Long-COVID patients show 86% with new onset cognitive fog (using validated criteria) and 48% with depression (PHQ8 criteria). Cognitive fog was the most common complaint endorsed by patients during their clinic evaluations. ***Additionally, a subgroup of patients requesting a behavioral evaluation, who were in the prime of their adult productivity, reported that "cognitive fog" was the main symptom impacting their functioning, work performance, and life satisfaction; making it a critical domain to target clinically.*** The specific cognitive deficits reported as part of this "fog" varied across patients.

In a pilot study, we prescribed 90 of these depressed patients a coached digital cognitive behavioral therapy (dCBT) app developed by UPMC called RxWell, as part of care. Half of the patients (N = 45) downloaded the app and the 75% who completed techniques showed improvement in depression over 3 months (large effect size of change with PHQ8 (delta 6; p=0.001; Cohen's d=1.1; mean age 46)).

We posit rapid, accurate, and scalable assessment of cognitive impairment and implementation of the right interventions targeting specific deficits is a better fuller recovery path for these patients. ***This proposal evaluates the utility of computer-based evaluation of COVID-related cognitive fog and the relative efficacy of two intervention strategies to treat moderate cognitive impairment using a randomized trial which will inform the design of a future adaptive trial.*** We plan to study 120 post-COVID patients seen in the Long-COVID clinic over the next 12 months with moderate or severe cognitive fog to assess the type and severity of neurocognitive impairment using computerized neuropsychological testing (BrainCheck). We will randomize to either 1) dCBT with coaching (RxWell) versus 2) stimulant medication (amphetamine/dextroamphetamine), as part of the study embedded in clinical care, to provide data to inform design of future larger phase adaptive trials. BrainCheck is

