an FDA-approved technology to provide rapid, mobile cognitive assessment with venture investment and partnership with UPMC Enterprises. RxWell is a mobile app, developed and housed at UPMC Health Plan, with health coaches employed by UPMC. Both technology solutions improve access in an era of shortage of neuropsychologists and mental health providers. Stimulants have documented safety and effectiveness in helping neurocognitive deficits in conditions with similar deficit such as ADHD, post-concussion, and other inflammatory medical conditions.

We will evaluate effects of treatments on **cognitive impairment (primary aim)** and emotional distress (depression), satisfaction with life, work disability and health care utilization (secondary outcomes) over 3 months. Findings will provide inform and guide the design for the next phase adaptive clinical trial. These results will be generalizable to treating other common neuroinflammatory cognitive deficits such as that which follows ICU admission for sepsis or respiratory failure or following chemotherapy.

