#### **Interventions:**

1. RxWell is a mobile application that consists of CBT techniques and a health coach who provides in-app guidance and risk mitigation. Coaches will receive training to provide cognitive rehabilitation tips. Usage will be tracked.
2. Standardized dosing of amphetamine/dextroamphetamine monitored monthly with response-based titration to maximum dose of 20 mg bid with side effects tracked. To date, patients with post-COVID fog have tolerated stimulants well.

Clinical flow and recruitment rates for registry study make 12-month recruitment completion feasible.

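### The Aim 1 models make no allowance for coach clustering in the dCBT arm, so the standard error of the arm contrast is understated if the coach ICC exceeds zero

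*Combined protocol and SAP*

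**What the plan says.** The *Interventions* section describes RxWell as CBT techniques plus "a health coach who provides in-app guidance and risk mitigation", and adds: "Coaches will receive training to provide cognitive rehabilitation tips". The *Project Summary* describes the app as housed at the health plan, "with health coaches employed by UPMC". The problem statement also links the coaches to the cognitive rehabilitation content of this arm. The coaches are therefore plural, and they deliver material aimed at the primary outcome.

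The comparator is a stimulant, "monitored monthly with response-based titration", with no coach.

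The *Project Summary* sets the size: "We plan to study 120 post-COVID patients seen in the Long-COVID clinic over the next 12 months". The *Summary of Project* says patients are "assigned with a 1:1 allocation to either arm using a permuted block design stratified by depression severity", which gives about 60 per arm.

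Under *Primary outcome: Cognitive impairment*, the Aim 1 analysis is intent-to-treat. The three-month outcome is analysed with "linear regression models with assigned intervention depression severity and the corresponding baseline score as independent variables". The longitudinal mixed model lists time, intervention, depression severity and baseline score, and does not state its random effects. App usage will be tracked, but coach identity is not mentioned. The plan does not give the number of coaches, how patients are assigned to them, or an ICC.

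**The concern.** Patients are randomised individually, but those in the dCBT arm are then grouped under whoever coaches them. If coaches differ in skill or style, patients of the same coach will have correlated outcomes, and the dCBT mean will carry coach-to-coach variation. That variation averages out over the number of coaches, not over 60 patients. Because coaches exist in only one arm, it falls directly on the treatment contrast. An ordinary regression that ignores it gives intervals that are too narrow and a false-positive rate above nominal.

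Aim 2 is also affected. It plans to use Aim 1 findings in simulations of sample size and operating characteristics for the adaptive trial. If coach identity is not captured while patients are being treated, the coach variance may be impossible to recover afterwards. Simulations that omit a non-zero coach variance would overstate power.

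**Working it through.** The plan gives no alpha, power, SD or target difference for the sample of 120, so there is no stated figure to reproduce. A two-sided 5% test is assumed for illustration.

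**Inputs from the documents:** 120 patients at 1:1, so 60 per arm; coaches in the dCBT arm only; 45 of 90 pilot patients (50%) downloaded the app.

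**Assumed inputs:** K coaches with equal caseloads; ICC ρ of the outcome within coach from 0 to 0.10; equal total variance in both arms.

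**Formulas.** Let c be the number of the 60 dCBT patients who are coached, and m = c/K the caseload.

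- dCBT-arm design effect: DE = 1 + (c/60)(m − 1)ρ. The stimulant arm has DE = 1.
- True SE / reported SE: r = √[(DE + 1)/2].
- True error of the nominal 5% test: 2[1 − Φ(1.96/r)].

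**Example, all 60 coached, K = 4, ρ = 0.05.** m = 15; DE = 1 + 14 × 0.05 = 1.70; r = √(2.70/2) = 1.16; error = 9.2%.

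**Example, 30 of 60 coached, K = 4, ρ = 0.05.** m = 7.5; DE = 1 + 0.5 × 6.5 × 0.05 = 1.163; r = √(2.163/2) = 1.04; error = 5.9%.

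True error of a nominal 5% test (SE ratio r in brackets):

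| Coached | Coaches | ρ = 0 | ρ = 0.02 | ρ = 0.05 | ρ = 0.10 |
|---|---|---|---|---|---|
| 60 of 60 | 4 | 5.0% (1.00) | 6.6% (1.07) | 9.2% (1.16) | 13.3% (1.30) |
| 60 of 60 | 6 | 5.0% (1.00) | 6.0% (1.04) | 7.7% (1.11) | 10.4% (1.20) |
| 60 of 60 | 10 | 5.0% (1.00) | 5.6% (1.02) | 6.5% (1.06) | 8.0% (1.12) |
| 30 of 60 | 4 | 5.0% (1.00) | 5.4% (1.02) | 5.9% (1.04) | 6.9% (1.08) |
| 30 of 60 | 6 | 5.0% (1.00) | 5.2% (1.01) | 5.6% (1.02) | 6.2% (1.05) |
| 30 of 60 | 10 | 5.0% (1.00) | 5.1% (1.00) | 5.3% (1.01) | 5.6% (1.02) |

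Outside this grid, with all 60 coached, 2 coaches and ρ = 0.10 give 21.1% (r = 1.57), while 20 coaches and ρ = 0.05 give 5.6% (r = 1.02).

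**Check by simulation.** With 20,000 trials per setting, all 60 coached and a pooled t-test, 4 coaches give about 7%, 9% and 13% at ρ = 0.02, 0.05 and 0.10, in line with the formula.

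**Within a depression stratum.** The Aim 1 hypothesis also concerns contrasts within depression groups. With about 30 per arm in a stratum, all coached, 4 coaches and ρ = 0.05: m = 7.5; DE = 1 + 6.5 × 0.05 = 1.325; r = 1.08; error = 6.9%.

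**Power, relevant to Aim 2.** Without clustering, 60 per arm gives 80% power at a standardised difference of (1.960 + 0.842)√(2/60) = 0.51. With the correct standard error, power is Φ(2.802/r − 1.960). With all 60 coached and ρ = 0.05, this is 67% for 4 coaches and 75% for 10.

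**The case against.** The strongest reply is that the size of the problem rests on figures the documents do not contain. A reader might infer several stronger statements that the text does not support:

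- *That there are only a few coaches.* No number is given, and with many coaches the effect is slight.
- *That every dCBT patient is treated through a coach.* The arm is an app with in-app guidance. Half the pilot patients never downloaded it, and under intent-to-treat such patients still count in the arm. At 50% uptake the inflation shrinks to at most about 7% on the main grid. The pilot figure need not carry over, because those patients were prescribed the app as part of care and the trial requires smartphone access, but full exposure cannot be taken as given.
- *That the standard errors are in fact too small.* This is true only if the coach ICC is above zero.
- *That the longitudinal model assumes independence between patients of the same coach.* Its random effects are not stated, so it is silent on coach.
- *That the Aim 2 simulations will overstate power.* No simulation model is specified. This follows only if a real coach variance is left out.

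Two further objections stand in part. Assignment is not described; if coaches are pooled or rotate, simple nesting is the wrong structure. The stimulant arm is also monitored by people, and the number of prescribers is not given, so clustering there cannot be excluded.

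These points limit the size and the certainty. They do not remove the omission: shared coaches deliver part of one arm, the three-month model lists its terms without coach, and there is no provision to record who coached whom.

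**Conclusion.** The concern holds in conditional form. Any positive coach ICC makes the three-month regression anti-conservative for the arm contrast. With 4 to 10 coaches and an ICC of 0.02 to 0.10, the true error of a nominal 5% test is about 5.6% to 13% with all 60 dCBT patients coached and about 5.1% to 7% with 30 coached. The true standard error exceeds the reported one by about 2% to 30% and 0.5% to 8% respectively. With an ICC of zero there is no inflation.

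These ranges rest on assumed coach numbers, equal caseloads, one coach per patient and a normal approximation, which leaves out the loss of degrees of freedom when coaches are few. The documents do not show that the reported standard errors will be wrong. They show that the plan could neither detect nor correct the problem if it is there. This is an inexpensive improvement, but the data have to be captured during the trial.

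**What to change.** 1. Record coach ID for every dCBT patient, including any change of coach. State in the plan how many coaches there are and how patients are assigned to them.
2. Prespecify a partially nested mixed model: a random coach effect in the dCBT arm only, separate residual variances by arm, and small-sample degrees of freedom (Satterthwaite or Kenward–Roger). Report it beside the stated regression, at least as a sensitivity analysis. dCBT patients who never have a coach stay in the analysis as clusters of one. If coaches turn out to rotate, adapt the random-effect structure to the recorded pattern. State the random effects of the longitudinal model at the same time.
3. Report the coach ICC with its interval, and run the Aim 2 simulations over a range of values, because a single estimate from this trial will be imprecise.

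The cost is one data field and one model term. Intervals will be somewhat wider, and with few coaches the variance will be poorly estimated; with three or four, small-sample degrees of freedom reduce the error inflation but may not remove it entirely. Spreading patients over more coaches would help where the service allows it, but it is an operational change and not a requirement. Logging the prescriber in the stimulant arm in the same way is optional and would let clustering there be checked.
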